8.2 Quality Assurance Audit

Study sites, the study database, and study documentation may be subject to a Quality Assurance audit during the course of the study by R-Pharm International or R-Pharm International's designee on behalf of R-Pharm International. In addition, inspections may be conducted by regulatory bodies at their discretion.

9. STATISTICS

9.1 Determination of Sample Size

All subjects who previously completed 24 weeks of double-blind treatment in the core studies will be eligible to enroll in this OLE study. It is estimated that approximately 1880 subjects will be randomized in the OLE study to 1 of 2 treatment groups (OKZ 64 mg q4w or OKZ 64 mg q2w) in a 1:1 ratio.

9.2 Data to be Analyzed

Data handling will be the responsibility of R-Pharm International's designee. The data will be inspected for inconsistencies by performing validation checks.

9.3 Analysis Populations

- Safety Population: The Safety population will include all subjects who receive at least 1 dose of study treatment during the OLE study. Subjects in the Safety population will be analyzed according to the treatment they actually received.
- A combined analysis of safety data from all subjects participating in the core studies and the OLE study will be conducted separately and details will be included in a separate Statistical Analysis Plan (SAP) for an Integrated Summary of Safety (ISS).
 Results of the ISS will be reported separately and will not be included in the Clinical Study Report of this study.
- Modified Intent-to-Treat (mITT) Population: The mITT population will include all subjects who sign an ICF for participation in the OLE study, are randomized in the OLE study, and receive at least 1 dose of study treatment in the OLE study. Subjects will be analyzed according to the treatment group to which they were randomized in the OLE study. The mITT population will be the primary efficacy analysis population.
- Per Protocol (PP) Population: The PP population will include all mITT subjects who do not have any major protocol violations. Subjects will be analyzed according to the OLE treatment group to which they were randomized. Major protocol violations and the inclusion of subjects in the PP population will be finalized prior to database lock. The PP population will be used for supportive analyses of selected efficacy endpoints.

9.4 Statistical Methods

This section provides a high-level description of the analyses planned in this study. Details of any analysis, interim or final, will be specified in the SAP, to be written and finalized prior to database lock. The statistical analysis will be performed by R-Pharm International's designee. All statistical analyses will be conducted using SAS® version 9.2 or higher for Windows.

All data collected in the clinical database will be presented in subject data listings.

Data collected after the modification of background therapy (as described in Section 6.13.3) will be used in all analyses.

Data collected during the core studies for subjects enrolled in the OLE study may be programmatically combined with the OLE study database for selected analyses.

All analyses of safety and efficacy will be descriptive; no inferential analyses will be performed.

Continuous endpoints will be summarized using descriptive statistics such number of available values (n), mean, median, minimum, maximum, and standard deviation in each treatment group and overall, as appropriate. Categorical endpoints will be summarized by the number and percentage of subjects in each category.

Data will be summarized based on treatment groups reflecting randomized or actual treatment (for efficacy or safety analyses, respectively) during the core and OLE studies as follows:

- a. OKZ 64 mg q4w (OLE): All subjects in the OKZ 64 mg q4w group in the OLE
- b. OKZ 64 mg q2w (OLE): All subjects in the OKZ 64 mg q2w group in the OLE
- c. OKZ 64 mg q4w (core/OLE): Subjects from the OKZ 64 mg q4w group in the core study and continuing on OKZ 64 mg q4w in OLE. For subjects enrolling from the CL04041025 core study, inclusion in the OKZ 64 mg q4w group in the core study will be based on the initial treatment period prior to Week 16 (i.e., placebo subjects re-randomized to receive OKZ 64 mg q4w at Week 16 will not be included in this group).
- d. OKZ 64 mg q2w (core/OLE): Subjects from the OKZ 64 mg q2w group in the core study and continuing on OKZ 64 mg q2w in OLE. For subjects enrolling from the CL04041025 core study, inclusion in the OKZ 64 mg q2w group in the core study will be based on the initial treatment period prior to Week 16 (i.e., placebo subjects

re-randomized to receive OKZ 64 mg q2w at Week 16 will not be included in this group).

- e. Placebo OKZ 64 mg q4w (OLE): Subjects from the placebo group in the core studies CL04041022 and CL04041023 that are assigned to the OKZ 64 mg q4w in the OLE.
- f. Placebo OKZ 64 mg q2w (OLE): Subjects from the placebo group in the core studies CL04041022 and CL04041023 that are assigned to the OKZ 64 mg q2w in the OLE.
- g. Placebo OKZ 64 mg q4w (core/OLE): Subjects from the placebo group in the core study CL04041025 (through Week 14) that are re-randomized to the OKZ 64 mg q4w group starting at Week 16 of the core study and continuing on OKZ 64 mg q4w in OLE.
- h. Placebo OKZ 64 mg q2w (core/OLE): Subjects from the placebo group in the core study CL04041025 (through Week 14) that are re-randomized to the OKZ 64 mg q2w group starting at Week 16 of the core study and continuing on OKZ 64 mg q2w in OLE.
- i. Adalimumab OKZ 64 mg q4w (OLE): Subjects from the adalimumab group in the core study CL04041023 that are assigned to the OKZ 64 mg q4w group in the OLE.
- j. Adalimumab OKZ 64 mg q2w (OLE): Subjects from the adalimumab group in the core study CL04041023 that are assigned to the OKZ 64 mg q2w group in the OLE.

Subjects are considered to be part of the placebo group during the core study if they are randomized to or receive placebo as their overall study treatment, and not as monthly placebo injections administered to maintain the blind in the OKZ 64 mg q4w treatment groups.

Note that treatment groups (c) through (j) are mutually exclusive; treatment groups (a) and (b) are aggregates representing all subjects treated with a specific OKZ regimen during the OLE study, regardless of the treatment received during the core study.

Additional summaries of efficacy endpoints may be generated for subjects from each core study separately, which will be detailed in the SAP.

9.4.1 Definition of Baseline

Unless otherwise specified, data will be analyzed for changes from both Core Baseline and OLE Baseline values. The Core Baseline value for each parameter will be defined as the baseline value from the core study (i.e., the last available measurement prior to the first dose

of study treatment in the core study). The OLE Baseline value will be defined as the last available measurement prior to the first OLE dose of study treatment. For subjects from Study CL04041025 who receive placebo through Week 14 and are re-randomized to OKZ starting at Week 16 (groups [g] and [h] as defined in Section 9.4), additional analysis of change from the last pre-OKZ value (prior to the first dose of OKZ at Week 16) will also be performed.

9.4.2 Disposition of Study Subjects

Disposition of study subjects will be summarized by treatment group (defined in Section 9.4) as the number and percentage of subjects enrolled (signed ICF for participation in the OLE study), randomized in the OLE study, included in each analysis population as defined in Section 9.3, completing the study treatment, and discontinuing from the study treatment overall and by reason for discontinuation, as well as completing the Safety Follow-Up Period or discontinuing during the Safety Follow-Up Period. The number and percentage of subjects discontinuing study treatment by visit in each treatment group will also be summarized.

A Kaplan-Meier plot of time to treatment discontinuation in each treatment group will be presented, where the time to treatment discontinuation will be calculated as the number of days from randomization at enrollment in the OLE study to the last dose of OLE study treatment. Subjects who complete the open-label Treatment Period as planned through Visit 10 (EoT/Week 106) will be censored on the date of their last dose in the OLE study.

Determination of major protocol deviations and inclusion of subjects in the analysis populations will be finalized and approved by R-Pharm International prior to database lock.

9.4.3 Demography and Baseline Characteristics

Demographic information and baseline characteristics collected at baseline of the core studies will be summarized for the treatment groups defined in Section 9.4. Key subject assessments at the time of enrollment in the OLE study (e.g., selected laboratory/safety assessments, ACR components, DAS28 [CRP], etc.) will also be summarized.

9.4.4 Prior and Concomitant Medications

Concomitant medications will be summarized as the number and percentage of subjects by World Health Organization (WHO) drug class, preferred name, and treatment group. Medications will be coded using the WHO Drug dictionary, Anatomic Therapeutic Class (ATC) level 2, and preferred drug name.

Any medication that a subject started before the first dose of OLE study treatment and continued to take during the OLE study, and any medication that the subject began taking after the first dose of the OLE study treatment, will be classified as concomitant.

Medications administered as a change in background therapy (as described in Section 6.13.3) will also be summarized as the number and percentage of subjects by WHO drug class, preferred name, and treatment group.

Medications administered concomitantly during the core studies or prior to the core studies may also be summarized.

9.4.5 Exposure and Compliance

Exposure to the OLE study treatment and compliance will be summarized descriptively by treatment group (see Section 9.4) for the Safety population based on treatment administration records in the Subject Diary and the return of used/unused study treatment (vials and/or PFS cartons) to the study site.

For a given study period, exposure to open-label study treatment will be calculated as the number of doses received during the open-label study period. The number of doses received will be calculated as a maximum of the number of injections recorded in the Subject Diary and the number of used vials and/or used PFS cartons returned by the subject to the study site.

Duration of exposure will be defined as the total number of days a subject was exposed to study treatment in the open-label Treatment Period, calculated as:

Date of last open-label dose – Date of first open-label dose + 1 day

Overall compliance (expressed as a percentage) will be calculated as:

(Exposure to open-label study treatment/number of doses subject was expected to receive) \times 100

Compliance will be calculated based on all planned doses (through completion or early discontinuation of treatment), as appropriate for each treatment group.

9.4.6 Safety Analyses

Analysis of safety endpoints (see Section 4.1) will be based on the Safety population. Subjects in the Safety population will be analyzed according to the treatment they actually received.

All safety and tolerability data recorded during the study will be listed and summarized descriptively by the treatment groups described in Section 9.4, and over time, as appropriate. No imputation for missing safety data will be performed. Further details will be provided in the SAP.

All continuous safety parameters will be summarized at each OLE visit in terms of actual values at each time point, changes from Core Baseline values, and changes from OLE Baseline values, as appropriate. All categorical safety parameters will be summarized in terms of number and percent of subjects in each category by OLE visit. Core Baseline and OLE Baseline values will also be summarized for reference. For subjects from Study CL04041025 who receive placebo through Week 14 and are re-randomized to OKZ starting at Week 16 (groups [g] and [h] as defined in Section 9.4), additional analysis of change from the last pre-OKZ value (prior to the first dose of OKZ at Week 16) will also be performed.

Major components for the safety analysis will include:

- TEAEs will be solicited at every study visit, recorded, and coded according to most recent version of the MedDRA.
- SAEs
- AESIs
- MACE
- Laboratory parameters
- Vital signs and physical examination findings
- ECG and other specialized test findings

In addition to the primary safety analysis, the incidence of AEs may be analyzed separately for subjects administered additional DMARDs (assigned as rescue medication during the core studies) and for subjects not receiving additional DMARDs as rescue medication.

9.4.6.1 Adverse Events

All AEs will be analyzed in terms of descriptive statistics and qualitative analysis. Adverse events will be listed for each subject and summarized by SOC and PT according to the latest version of the MedDRA. In addition, summaries of AEs by severity (evaluated using the CTCAE version 4.0) and relationship to study treatment will be presented.

An AE will be defined as treatment-emergent in the OLE study if its onset date or worsening in severity is on or after the date of first administration of the OLE study treatment. In cases

where only partial information is available for the onset date of an AE, available date components will be used to determine treatment-emergent status; in the case of ambiguity, AEs will be considered treatment-emergent.

The following summaries of subject incidence and number of events will be presented by the treatment groups defined in Section 9.4:

- Overall summary of TEAEs
- Summary of TEAEs by SOC and PT
- Summary of serious TEAEs by SOC and PT
- Summary of TEAEs leading to death by SOC and PT (if applicable)
- Summary of treatment-emergent AESIs (as defined in Section 7.4.3) by SOC and PT
- Summary of (adjudicated) MACE and individual MACE components
- Summary of TEAEs by SOC, PT, and maximum severity
- Summary of drug-related TEAEs by SOC and PT
- Summary of TEAEs leading to early treatment discontinuation by SOC and PT
- Summary of the most common TEAEs by PT (≥5% in any treatment group)
- Summary of TEAEs by Standardized MedDRA Queries narrow terms

Safety/tolerability and AE data will be presented in individual listings.

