PK blood samples	√ y												
ADAs	✓			✓		✓		✓		✓			
ANA and anti dsDNA antibody	✓					✓				✓			✓
Assess injection site reactions	✓	✓	✓	✓	✓	✓	✓	✓	✓				
TB risk questionnaire	✓			✓		✓		✓		✓		✓	
Chest X-ray ^z	✓					✓				✓			
12-lead ECG	✓					✓		✓		✓			✓

Assessments	OLE Baseline	Open-Label Treatment Period							ЕоТ	Safety Follow-Up Period			
Visit	1 ^a	2	3	4	5	6	7	8	9	10	SFU-1	SFU-2	SFU-3
Week	24	26	28	36	44	52	64	76	88	106 (+2b)	108 (+4b)	112 (+8b)	126 (+22b)
Visit Window (days)	±5	±5	±5	±5	±5	±5	±5	±5	±5	±5	±7	±7	±7
Subject Diary ^{aa}	✓	✓	✓	✓	✓	✓	✓	✓	✓	✓			

Abbreviations: ADA = antidrug antibody; AEs = adverse events; ALT = alanine aminotransferase; ANA = antinuclear antibody; ApoB = apolipoprotein B; ApoA1 = apolipoprotein A1; aPTT = activated partial thromboplastin time; AST = aspartate aminotransferase; BNP = brain natriuretic peptide; BP = blood pressure; CRP = C-reactive protein; CV = cardiovascular; dsDNA = double-stranded DNA; ECG = electrocardiogram; EoT = End of Treatment; EQ-5D = European Quality of Life-5 Dimensions; ESR = erythrocyte sedimentation rate; FACIT-Fatigue = Functional Assessment of Chronic Illness
Therapy-Fatigue Scale; GGT = gamma-glutamyl transferase; HAQ-DI = Health Assessment Questionnaire-Disability Index; HbA_{1c} = glycosylated hemoglobin; HDL = high-density lipoprotein; IEC = Independent Ethics Committee; IGRA = interferon-gamma release assay; INR = international normalized ratio; IRB = Institutional Review Board; IWRS = Interactive Web Response System; LDL = low-density lipoprotein; NT-proBNP = N-terminal pro-hormone of brain natriuretic peptide; OKZ = olokizumab; OLE = open-label extension; PFS = pre-filled syringe(s); PK = pharmacokinetic(s); PRO = patient-reported outcomes; RBC = red blood count; SAE = serious adverse event; SC = subcutaneous(ly); SF-36 = Short Form-36; SJC = swollen joint count; TB = tuberculosis; TJC = tender joint count; WBC = white blood count; WPS-RA = Work Productivity Survey - Rheumatoid Arthritis; VAS = Visual Analog Scale.

- a. All subjects will begin the OLE study at Visit 1. The baseline visit for the OLE study is the same visit as the Week 24 visit in the core studies.
- b. The number of weeks (+2, +4, +8, or +22) after the last dose of the study treatment.
- c. Complete physical examination should be performed at these visits (Section 7.4.7.1).
- d. Vital signs include temperature, heart rate, BP, and respiratory rate.

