7.2 Pharmacokinetics

There will be no collection of blood samples for the determination of OKZ concentration in plasma in this study.

• The Week 24 sample is the last sample to be collected in the core studies. This sample must be collected prior to administration of OKZ in the OLE study, and the sample will be analyzed and included in the data set of the core study in which the subject participated, according to the procedures detailed in the core study protocol. This sample will not be analyzed as part of the OLE data set.

To provide documentation that the Week 24 PK sample was collected prior to the first dose of study treatment in this study, the date and time of OKZ administration at Week 24 will be captured in each subject's eCRF.

Although there will be no collection of blood samples in this study for the determination of OKZ concentration in plasma, blood samples that are collected for immunogenicity analysis (see Section 7.3) may also be used to determine OKZ concentrations in plasma if it is

determined that such evaluation may provide additional information regarding subject safety and efficacy of OKZ (e.g., due to unexpected immunogenicity results).

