Any clinically significant findings from laboratory test results, vital sign measurements, other procedures, etc. should be reported to R-Pharm International's designee via eCRF, EDC, and/or designated data transmission methods. Investigators should use correct medical terminology/concepts when recording AEs on the AEs eCRF page, avoiding colloquialisms and abbreviations. Only 1 AE term should be recorded in the event field on the AEs eCRF page. For AEs other than injection-related reactions, a diagnosis (if known) should be recorded on the AEs eCRF page rather than individual signs and symptoms (e.g., record only liver failure or hepatitis rather than jaundice, asterixis, and elevated transaminases).

However, if a constellation of signs and/or symptoms cannot be medically characterized as a single diagnosis or syndrome at the time of reporting, each individual event should be recorded on the AEs eCRF page. If a diagnosis is subsequently established, all previously reported AEs based on signs and symptoms should be nullified and replaced by 1 AE report based on the single diagnosis, with a starting date that corresponds to the starting date of the first symptom of the eventual diagnosis.

Each AE is to be evaluated for date and time to onset, duration, severity, seriousness, and potential relatedness to the study treatment and/or study procedure (i.e., any procedure required by the study protocol). The action taken and the outcome must also be recorded in the AE page of the eCRF.

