7.4.7 Vital Signs, Physical Findings, and Other Safety Assessments

7.4.7.1 Physical Examination

A complete physical examination will be performed at Visit 1 (OLE Baseline/Week 24), Visit 6 (Week 52), Visit 10 (EoT/Week 106), and Safety Follow-Up Visit SFU-3 (Week 126), as indicated in Table 1. A complete physical examination will include

evaluation of general appearance, skin, head, eyes, ears, nose and throat, lymph nodes, respiratory, CV, GI including hepatobiliary assessment, musculoskeletal, endocrine system, neurological systems, and urogenital system.

At all other visits, a partial physical examination will be performed assessing the following: general appearance, skin (including site of study treatment injection), respiratory, CV, and GI.

All significant findings that are present at OLE Baseline must be reported on the "Adverse Events Ongoing from Core Study" page of the eCRF. Significant findings detected after randomization to the OLE study that meet the definition of an AE must be recorded on the relevant "Adverse Event" page of the eCRF.

7.4.7.2 *Vital Signs*

Vital signs (temperature, heart rate, BP, and respiratory rate) will be measured as indicated in Table 1, and when clinically indicated. Whenever possible, vital sign assessments should be performed by the same study site staff member and using the same validated device(s) throughout the study. Blood pressure and heart rate should be measured after the subject rests 5 minutes in a sitting position.

Not every vital sign abnormality qualifies as an AE. A vital sign result should be reported as an AE if it meets any of the following criteria:

- Results in a change in RA treatment (e.g., dosage modification, treatment interruption, or treatment discontinuation)
- Results in a medical intervention or a change in concomitant therapy
- Clinically significant in the Investigator's judgment

It is the Investigator's responsibility to review all vital sign findings. Medical and scientific judgment should be exercised in deciding whether an isolated vital sign abnormality should be classified as an AE.

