7.4.7.5 Electrocardiogram

A standard 12-lead ECG will be performed at the time points specified in Table 1.

Subjects should rest in a supine position in a controlled, calm environment for at least 15 minutes prior to the recording and should be motionless during the recording.

The Investigator (if certified) or a certified designee will evaluate whether the ECG is normal or abnormal and whether it is clinically significant, if abnormal. Clinically relevant abnormalities, including the baseline ECG, should be recorded on the AE eCRF page.

All ECG records collected during the study should have a printed copy kept as a source document at the study site (if the ECG record is printed on thermal paper, a photocopy should be made).

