9.4.6.1.1 Analysis of Treatment-Emergent Adverse Event Rates per 100 Patient-years of Follow-up

Summaries of TEAEs occurring in subjects in the safety population of this OLE study will also be provided based on combined AE data from the core studies and the OLE study, attributing each TEAE to the last study treatment received at/before the AE onset. In other words, an AE will be defined as treatment-emergent under a given study treatment (OKZ 64 mg q4w, OKZ 64 mg q2w, placebo, or adalimumab) if AE's onset date is on or after the date of first dose the corresponding treatment and prior to initiation of the next study treatment, if any (e.g., OKZ after placebo or adalimumab). In order to account for differences in the duration of exposure and follow-up under each study treatment and across subjects, subject IRs and ERs will be summarized per 100 subject-years (SY) of follow-up (/100 SY) based on the OLE safety population and presented by study treatments as follows:

- i. OKZ 64 mg q4w: subjects receiving OKZ 64 mg q4w during the core study or OLE. Only those TEAEs that first occur or worsen in severity after the first administration of OKZ 64 mg q4w (either in the core or OLE study) will be counted.
- ii. OKZ 64 mg q2w: subjects receiving OKZ 64 mg q2w during the core study or OLE. Only those TEAEs that first occur or worsen in severity after the first administration of OKZ 64 mg q2w (either in the core or OLE study) will be counted.
- iii. Placebo: subjects receiving placebo during the core study. Only those TEAEs that first occur or worsen in severity after the first administration of placebo and prior to administration of OKZ will be counted. Subjects are considered as receiving placebo during the core study if they are receiving placebo as their overall study treatment, and not as monthly placebo injections administered to maintain the blind in the OKZ 64 mg q4w group.
- iv. Adalimumab: subjects receiving adalimumab as active control study treatment during the core study CL04041023. Only those TEAEs that first occur or worsen in severity after the first administration of adalimumab and prior to administration of OKZ will be included.

The following summaries will be provided:

- IRs (/100 SY) and ERs (/100 SY) for TEAEs overall and by SOC
- IRs (/100 SY) and ERs (/100 SY) for SAEs overall and by SOC and PT
- IRs (/100 SY) and ERs (/100 SY) for AESIs overall and by SOC and PT

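### Under the date-only rule in 9.4.6.1, findings made before dosing at Visit 1 count as OLE treatment-emergent, and 9.4.6.1.1 gives conflicting rules for that same day

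*Combined protocol and SAP*

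**What the plan says.** Section 9.4.6.1 sets the rule for the OLE adverse-event tables: "An AE will be defined as treatment-emergent in the OLE study if its onset date or worsening in severity is on or after the date", where the day meant is that of the first OLE dose. The unit is the calendar date. For onset dates that are only partly known, the paragraph adds that "in the case of ambiguity, AEs will be considered treatment-emergent".

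Footnote a to Table 1 (Section 5.1) says: "The baseline visit for the OLE study is the same visit as the Week 24 visit in the core studies". Section 5.4.1.1 lists the physical examination, ECG, chest X-ray, coagulation, lipid, chemistry and hematology assessments for that visit and puts the injection last. Sections 7.4.1 and 7.4.5 start OLE adverse-event recording at Visit 1, not at the first injection. Sections 7.4.1 and 7.4.6 make a clinically significant laboratory abnormality an adverse event.

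Two sections say where baseline findings are recorded. Section 7.4.7.5: "Clinically relevant abnormalities, including the baseline ECG, should be recorded on the AE eCRF page". Section 7.4.7.1: "All significant findings that are present at OLE Baseline must be reported on the" *Adverse Events Ongoing from Core Study* page, with the adverse-event page kept for findings made after OLE randomization.

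For the combined rates, Section 9.4.6.1.1 first assigns each event to the treatment most recently received when it began. It then restates this by date: an event is treatment-emergent under a treatment "if AE's onset date is on or after the date of first dose the corresponding treatment" and before the next treatment starts. Items (i) and (ii) count only events after the first OKZ injection. Items (iii) and (iv) count comparator events that arise before OKZ is given. Placebo and adalimumab follow-up stops on the day before OKZ starts.

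**The concern.** A date rule does little harm when few findings are made on the dosing day before the injection. Here every subject has a full assessment visit on exactly that day, and it closes the core study. An abnormality first seen at 09:00 and entered with that day's date arose under the core treatment, yet the rule labels it as emerging under OLE treatment.

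Long-term safety is the primary objective (Section 3.1). In the OLE tables, all groups can acquire day-1 events that precede the first OLE dose. In the combined rates the more serious risk concerns former placebo subjects from CL04041022 and CL04041023 and former adalimumab subjects, because a finding that precedes any OKZ exposure can be counted against OKZ. The time-to-first-event analyses of MACE and malignancy (9.4.6.1.2, 9.4.6.1.3) also take events that are treatment-emergent under OKZ, so they inherit whichever reading is used.

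**Working it through.** The plan states no figure on this point, so the check applies its rules to test cases.

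**1. Three onsets around a hypothetical first injection at 11:00 on the Visit 1 date**

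| Recorded onset | 9.4.6.1 date rule | 9.4.6.1.1 date sentence, OKZ | 9.4.6.1.1 items (i)–(ii), OKZ |
|---|---|---|---|
| Day before | no | no | no |
| Same day, 09:00 (pre-dose ECG) | yes | yes | no |
| Same day, 12:00 | yes | yes | yes |

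The rules disagree only on the same-day pre-dose finding. A complete Visit 1 date is not a partial date, so the tie-break for ambiguous dates is not even reached in 9.4.6.1.

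**2. The same finding in the combined rates, for a former placebo or adalimumab subject**

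- *Date sentence.* The event adds 1 to the OKZ numerator s_j. Its truncated follow-up c_ij is onset date minus first-dose date, which is 0 days. Without it, a completer could contribute up to (104 − 24) × 7 + 155 = 715 days, or 715 / 365.25 = 1.96 years. A later, genuine first event of the same term is then not counted in s_j. In the event rate, the numerator rises by 1 and the denominator is unchanged.
- *Attribution principle and items (iii)–(iv).* The event belongs to the comparator. Comparator follow-up ended the day before, so the event lies one day outside the time it is divided by.
- *Both at once.* The date sentence starts each treatment by date but ends it at initiation of the next treatment. If that end is read by clock time, the 09:00 event also qualifies under the comparator.

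**3. Recording route**

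A clinically relevant baseline ECG abnormality goes to the adverse-event page under 7.4.7.5. Under 7.4.7.1, significant findings present at OLE Baseline go to the ongoing-from-core page. Section 5.4.1.1 lists randomization ahead of the Visit 1 assessments, so a finding can be both present at OLE Baseline and detected after randomization. It then meets both routes within 7.4.7.1.

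**4. Who is affected**

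- Section 7.4.5 re-records an event that began in the core study only if it worsens. The rule therefore bites on newly detected findings given the Visit 1 date, and on worsening dated that day.
- Subjects already on OKZ by Week 24, including CL04041025 placebo subjects re-randomized at Week 16, stay under OKZ in the combined rates on either reading. For them only the OLE tables change.
- Section 9.4.1 takes the last pre-dose value as OLE Baseline, and 9.4.6.2 counts chemistry and hematology abnormalities after the first dose. Those tables are not affected. It follows that one Visit 1 value can be the baseline in the laboratory tables and an emergent event in the adverse-event tables.

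**The case against.** The best defence is that a date rule leaning towards treatment-emergent is a cautious convention, that all analyses are descriptive (Section 9.4), and that 9.4.6.1.1 already states the right principle. The last point stands in part. A reader might infer that the comparator column cannot hold a switch-day pre-dose event at all. The documents do not support that: the attribution principle and items (iii)–(iv) place the event there. The defect is conflicting wording plus a follow-up cut-off that omits the switch day. The caution argument is weaker, because a rule that moves comparator findings to OKZ is not cautious for a comparison of columns.

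A second defence is that the date of detection need not be the date of onset. This also stands. Section 7.4.5 dates a diagnosis from its first symptom, and known core-study events are re-recorded only on worsening. It would be too strong to say that continuing OKZ subjects have their existing core events counted afresh.

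Third, 7.4.7.1 is the physical-examination section and may cover examination findings only. On that reading 7.4.7.5 does not contradict it; the two sections simply treat baseline findings differently. The ECG instruction still sends a pre-dose finding to the adverse-event page.

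Finally, a reader might assume that adverse-event clock time is available. Dose time is: "the date and time of OKZ administration at Week 24 will be captured in each subject's eCRF". For events, Section 7.4.5 says "Each AE is to be evaluated for date and time to onset", which can mean latency, and elsewhere the section asks only for dates of onset. The repair cannot depend on event times alone.

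**Conclusion.** The point holds in this form. In the OLE tables, 9.4.6.1 as written makes a newly detected pre-dose finding with the Visit 1 date treatment-emergent. In the combined rates, 9.4.6.1.1 gives two answers for a switch-day pre-dose event in former placebo (CL04041022, CL04041023) and adalimumab subjects, and neither is sound: one charges OKZ, the other puts the event outside the comparator's follow-up time.

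The size cannot be computed from the documents. Applying an assumed share of 1% to 5% to the 1880 planned subjects gives 0.01 × 1880 ≈ 19 to 0.05 × 1880 = 94 subjects. The documents give no such share, and 1880 is the wrong base for misattribution to OKZ, which concerns only the former placebo and adalimumab subjects, whose number is not stated. What can be said is the effect per event (working, step 2) and its direction under the date wording, which is from comparator to OKZ. The conclusion assumes that sites enter such findings with the Visit 1 date; findings back-dated into the core study are not affected.

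**What to change.** 1. Use one rule in 9.4.6.1 and 9.4.6.1.1: onset or worsening after the first administration of the treatment concerned. Flag findings from Visit 1 pre-dose assessments as not treatment-emergent for the OLE unless they worsen after dosing, and assign them to the preceding core treatment. Use clock time where it is recorded. Keep first-day events of truly unknown timing as treatment-emergent.
2. End placebo and adalimumab follow-up at the first OKZ administration, so that numerator and denominator cover the same period. This changes person-time by at most about a day per subject.
3. Reconcile 7.4.7.5 with 7.4.7.1 so that OLE Baseline ECG abnormalities go on the *Adverse Events Ongoing from Core Study* page, and make clear that findings from Visit 1 pre-dose assessments follow that route even though randomization is listed earlier in the visit.

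The cost is protocol and SAP wording, one data flag and one programming rule, all feasible before database lock. A few first-day events without usable timing will remain ambiguous.
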